The Tanglewood Trail walking group is a community-initiated walking group, spontaneously established in summer 2016 and continued with UK IRB-approved structure and support in 2017. Community members meet at the Housing Authority in Whitesburg, KY and walk the approximately 1 kilometer Tanglewood Trail connecting the Housing Authority to the Farmer's Market. In 2017, participants that walked to the Farmer's Market received a \$10 voucher on Saturdays during the season (June-October). Adults 18 years and older received one voucher each time they walk. While this program was initiated by community members and UK researchers were not involved with its creation or tracking any component of the program, UK researchers became involved in the summer of 2017. This partnership was strengthened and, following IRB-approval, will continue into the 2018 season with another Walking Group and an extension of the Walking Group beyond the Farmer's Market season as a feasibility study and new name: Fresh Steps. The current proposed study will target non-pregnant healthy, 18+ years old, community members who are willing and able to walk the Tanglewood Trail on Saturday mornings, June-September 2018 and willing and able to walk 1 mile at the Cowan Community Center, October 2018 – February 2019. All participants will receive \$10 to spend on fruits and vegetables at the Farmer's Market, June-September, and a \$20 healthy prepared meal from CANES kitchen October-February. An additional control group (in nearby Harlan county) will be added. The control group will only receive monthly nutrition education via home mail or e-mail. We hypothesize that adults who regularly attend the walking group and subsequently purchase fruits and vegetables at the Farmer's Market (June-September) and consume a healthy prepared meal (October-February) will experience an increase in physical activity, fruit and vegetable intake, and community engagement, and an improvement in anthropometrics and biomarkers associated with adulthood chronic disease (including cholesterol, hemoglobin A1c, blood pressure, carotenoid status, weight, and waist circumference).

Objectives: List your research objectives. You may reference grant application/sponsor's relevant protocol pages and attach as an appendix in the E-IRB "Additional Information" section.

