Specific Aim 1: Compare the short-term and long-term impact of the active intervention and control condition on healthy lifestyle behaviors (PA and nutritional patterns) associated with chronic disease risk reduction. Hypothesis 1: Participants in the active intervention whose levels of PA and F/V consumption are meeting national recommendations at baseline (BL) will be more likely to maintain these at 4 and 8 months than participants in the control group whose levels fall within national recommendations at baseline. Hypothesis 2: Participants in the active intervention whose levels of PA and F/V consumption not meeting national recommendations at BL will have greater improvement in PA and F/V consumption at 4 and 8 months compared to participants in the control group whose levels are not meeting national recommendations at BL. Specific Aim 2 Compare the short-term and long-term impact of the active intervention and control condition on anthropometric (weight and waist circumference) and biological (blood pressure (BP), HbA1c, and lipids) chronic disease risk factors. Hypothesis 1: Participants in the active intervention whose anthropometric and biological measures are within normal ranges at BL will be more likely to maintain these ranges throughout the period of the study than participants in the control group whose levels are within normal ranges at BL. Hypothesis 2: Participants in the active intervention whose anthropometric and biological measures outside of normal ranges at BL will have greater improvement in these measures at 4 and 8 months than participants in the control group whose levels are outside of normal ranges at BL.

Study Design: Describe the study design (e.g., single/double blind, parallel, crossover, etc.). Indicate whether or not the subjects will receive placebo medication at some point in the research procedures. Also, indicate whether or not the subjects will be randomized in this study. You may reference sponsor's protocol pages and attach as an appendix in the E-IRB "Additional Information" section. (Including the study design table from a sponsor's protocol is helpful to IRB members.)

Community-Based Participatory Research: If you are conducting community-based participatory research (CBPR), describe strategies for involvement of community members in the design and implementation of the study, and dissemination of results from the study.

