The sample population consists of a convenience sample that is participating in a pilot study. This study will focus on nonpregnant healthy adult (ages 18+) community members who walk the Tanglewood Trail on Saturdays, June-September 2018 and at Letcher County Recreation Center October 2018 – February 2019. Any interested community members who are 18 years or older, nonpregnant and able to voluntarily give their consent are welcome to join the study. Seventy-five participants will be recruited to participate in this project in Whitesburg ("walking group"), and seventy-five control participants will be recruited in Harlan ("control group"), who will only receive monthly nutrition education via e-mail or home mail. An information session for any potentially interested individuals will be held by the UK program manager with the help of the community leader following IRB approval. The 75 walking group participants will meet at the Housing Authority at a designated time each Saturday. When they arrive, they will be signed in by a community leader and receive a farmer's market voucher (see attached) for \$10. They will walk as a group to the farmer's market and hand their voucher to the market manager, who will give them \$10 in tokens to purchase fruits and vegetables at the market. The voucher will have two sides: one side will ask participants to check off what fruits and vegetables they ate over the past week, the second side will ask how participants used what they purchased at the market last week (ie. How much was eaten fresh vs. preserved) and how many steps they took over the past week, tracked using a pedometer provided at the baseline measurements in May 2018. They will turn the filled-out voucher in as they leave the market. During the meal preparation portion of the study, participants will complete weekly meal evaluation sheets. The walking group will receive 1) Education - nutrition education weekly via a combination of nutrition posts on Facebook (2/mo June – Sept), recipe and phytonutrient cards that includes a video recipe demonstration (1/mo), and recipe samples with cards (1/mo). Post-farmer's market: 1 weekly recipe demonstration (YouTube and offered live), recipes with nutrition/phytonutrient information to accompany meals (Oct – Jan); 2) Vouchers- weekly \$10 farmer's market vouchers (June – Sept), weekly \$20 healthy meal vouchers (Oct – Jan); 3) PA - 1 day/week community walk along Tanglewood Trail (June-Sept) and admission to Recreation Center (Oct – Jan), and 4) Activity trackers - a 3DTriSport pedometer. The 75 control group participants will receive monthly nutrition education via their choice of e-mail or home mail. Nutrition education will focus on phytonutrients, the importance of fruit and vegetable intake, how these factors might protect them from environmental pollutants, and healthy cooking. This nutrition education will also be provided to walking group participants via Facebook. Walking group participants will also have access to monthly Farmer's Market samples of Plate it Up Kentucky Proud recipes and recipe cards. No participants will receive medications – neither real nor placebo. Data for both the walking group and control group will be a time series collection of blood pressure, finger-stick total cholesterol, LDL, HDL, triglycerides, hemoglobin A1c (cardiocheck meter), height, weight, waist circumference, carotenoid status (carotenoid RS, which is a non-invasive instrument that is a reliable indicator of fruit and vegetable intake (see attached), Newest Vital Sign (NVS) rapid screening test for health literacy, and a survey (see attached). Measurements will be taken and surveys collected three times – baseline data will be collected in May 2018, mid-point data collected late September/early October 2018, and follow-up data collected in February 2019. Only walking group participants will receive pedometers and report weekly steps to the community leader at the Farmer's Market (June through September) or CANES Kitchen (October through February). Finger stick tests will be conducted by University of Kentucky employees who have completed all necessary biohazard training (see attached IBC approval and certificates of completion). Lysol wipes will be available to wipe down equipment as needed. Hand sanitizer will be provided to each researcher to use between glove changes. Gloves will be changed between each participant. Heat packets will be available for participants with cold hands to make the finger stick go faster and easier. Band-Aids will be provided after each stick. Lancets will be used to take the finger stick and all materials will be disposed of in sharps containers. All sharps containers will remain sealed until the research team returns to the University of Kentucky that same day to dispose of the sharps containers. Additionally, focus groups with walking group participants will be conducted in October 2018 and February 2019. Questions for the focus groups will be formulated out of 5-10 informant interviews conducted in July (with each interview lasting approximately 30 minutes – 1 hour). Participants for both interviews and focus groups will be recruited with the help of the market manager and community leader, and all participants will be informed that they are participating in the interviews and/or focus groups for research purposes and sign a consent form. Questions asked will assess program use, attitude/behavior change over the course of the program, social capital, and social cohesion.

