Based on walking group numbers from summer 2017 we anticipate a maximum enrollment of 75 walking group participants (18+ years old, nonpregnant) and 75 control participants. Previous research in Letcher County suggests the majority of participants will be white, ages 18-65, both male and female, of moderate health status. A prerequisite for participating in this study is the ability to walk 1 mile (assessed using the Exercise and Sports Science Adult Pre-Exercise Screening Tool, Stage 1 – see attached), nonpregnant, pre-supposing a baseline health status. Any interested community members over the age of 18 and in moderate or good health will be included. Since our focus is on changes in rates of chronic disease in adulthood, children will be excluded from study participation (but may walk with their parents). Institutionalized adults, pregnant adults, adults with impaired consent capacity, and prisoners will be excluded. No one will be excluded based on sex/gender or racial/ethnic identity. Seventy-five participants in Harlan County will be enrolled in the control group with the same inclusion/exclusion criteria as the walking group. Interview and focus group participants will include volunteers from the walking group. All participants will be informed that the interviews and focus groups are for research purposes, and sign a consent form.

Attachments

Subject Recruitment Methods & Privacy: Describe plans for the identification and recruitment of subjects, including how the population will be identified, and how initial contact will be made with potential subjects by those having legitimate access to the subjects' identity and the subjects' information. Describe the setting in which an individual will be interacting with an investigator. If applicable, describe proposed outreach programs for recruiting women and minorities as participants in clinical research.

Please note: Based upon both legal and ethical concerns, the UK Medical Institutional Review Board (IRB) will not approve finder's fees for research studies.

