Data for both the walking group and control group will be a time series collection of blood pressure, finger-stick total cholesterol, LDL, HDL, triglycerides, hemoglobin A1c (cardiocheck meter), height, weight, waist circumference, carotenoid status (carotenoid RS, which is a non-invasive instrument that is a reliable indicator of fruit and vegetable intake (see attached), and a survey (see attached). Measurements will be taken and surveys collected three times – baseline data will be collected in May 2018, mid-point data collected late September/early October 2018, and follow-up data collected in February 2019. Only walking group participants will receive pedometers and report weekly steps to the community leader at the Farmer's Market (June through September) or CANES Kitchen (October through February). During the meal preparation portion of the study, participants will complete weekly meal evaluation sheets. Finger stick tests will be conducted by University of Kentucky employees who have completed all necessary biohazard training (see attached IBC approval and certificates of completion). Lysol wipes will be available to wipe down equipment as needed. Hand sanitizer will be provided to each researcher to use between glove changes. Gloves will be changed between each participant. Heat packets will be available for participants with cold hands to make the finger stick go faster and easier. Band-Aids will be provided after each stick. Lancets will be used to take the finger stick and all materials will be disposed of in sharps containers. All sharps containers will remain sealed until the research team returns to the University of Kentucky that same day to dispose of the sharps containers. Additionally, focus groups with walking group participants will be conducted in October 2018 and February 2019. Questions for the focus groups will be formulated out of 5-10 informant interviews conducted in July (with each interview lasting approximately 30 minutes – 1 hour). Participants for both interviews and focus groups will be recruited with the help of the market manager and community leader, and all participants will be informed that they are participating in the interviews and/or focus groups for research purposes and sign a consent form. Questions asked will assess program use, attitude/behavior change over the course of the program, social capital, and social cohesion.

Attachments

Attach Type	File Name
DataCollection	Meal Evaluation.docx

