If yes, check below all that apply and attach the applicable document(s): [?](#)

- HIPAA De-identification Certification Form
- HIPAA Waiver of Authorization

[Attachments](#)

STATISTICAL ANALYSIS PLAN

This study will recruit approximately 150 participants, who will be divided into walking or non-walking groups to assess dietary behavior. Outcomes will compare the change in fruit and vegetable intake, health and exercise at baseline, 4 months and 8 months using survey metrics. Significance will be determined using a two-way ANOVA with a post-hoc Tukey's t-test; $p<0.05$.

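### The SAP's only test names no within-person term, response or deciding effect; run as an ordinary two-way ANOVA on raw scores, it loses most of its power for group-by-visit

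*Combined protocol and SAP*

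**What the plan says.** The Statistical Analysis Plan gives one inferential rule: "Significance will be determined using a two-way ANOVA with a post-hoc Tukey's t-test", with a threshold of p<0.05. The sentence before it describes the comparison: "Outcomes will compare the change in fruit and vegetable intake, health and exercise at baseline, 4 months and 8 months using survey metrics". No other section supplied gives an analysis method.

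The data are repeated measures. Study Design and Data Collection both state, for both groups, "Measurements will be taken and surveys collected three times". Safety Precautions says that survey data carry a code linked to the participant.

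In Objectives, each aim has two hypotheses. Hypothesis 2 of Aim 1 reads "Participants in the active intervention whose levels of PA and F/V consumption not meeting national recommendations at BL will have greater improvement" at 4 and 8 months, compared with control. Hypothesis 1 says that intervention participants who meet the recommendations at baseline "will be more likely to maintain these at 4 and 8 months than participants in the control group". Aim 2 repeats this pair for anthropometric and biological measures.

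The arms are two places. The opening background section says "An additional control group (in nearby Harlan county) will be added". Study Population says "we anticipate a maximum enrollment of 75 walking group participants", with 75 controls. Study Design adds: "The sample population consists of a convenience sample that is participating in a pilot study".

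**The concern.** Three things are missing from the rule, and each can change the result.

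- **Within-person term.** An ordinary two-way ANOVA treats three visits by one person as three people. Its single residual mixes between-person and within-person variation. That makes it too small a yardstick for the group main effect and too large a one for group-by-visit.
- **Response.** The SAP speaks of change but lists baseline among the time points. It does not say whether raw scores or changes enter the model.
- **Deciding effect.** A two-way ANOVA gives a group, a visit and an interaction test, and Tukey adds all pairs of cells. The SAP does not say which of these counts as success. On raw scores, greater improvement than control is the group-by-visit effect. The group main effect instead averages over baseline, so it carries any difference already present between the two counties.

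Hypothesis 1 asks a yes/no question (still within range or not), for which the SAP states no matching analysis.

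At stake is whether the trial's only significance rule can detect the effect that its hypotheses describe, and whether its result depends on which line of output is reported.

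**Working it through.** **Inputs from the documents.** 75 per arm (Study Design, Study Population), so 75 + 75 = 150, which agrees with the SAP total. Three visits. Alpha 0.05. The documents give no power, SD, effect size, within-person correlation or dropout, so there is no sample-size derivation to reproduce.

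**Assumptions.** SD 1; equal within-person correlation rho = 0.3/0.5/0.7/0.8 (compound symmetry); 75 per arm with full follow-up, a best case. Results below are in that order of rho. An ordinary ANOVA on raw scores has 450 records in 6 cells, so 444 error df.

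**1. Group main effect, null, raw scores.** True variance over assumed variance is 1 + 2·rho. Type I error = P(F(1,444) > 3.86/(1 + 2·rho)) = 12.1/16.5/20.5/22.4%. Simulation (20,000 trials per scenario) agrees to within about half a percentage point.

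**2. Group-by-visit, null, raw scores.** The ratio is 1 − rho. Type I error = P(F(2,444) > 3.02/(1 − rho)) = 1.4/0.3/0.0/0.0%. With a within-person term, simulation returns both tests to about 5%.

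**3. Group-by-visit power, assumed between-group effect 0/0.2/0.4 SD.** The interaction deviations are ±0.1, 0, ±0.1 over the six cells, so their sum of squares is 4 × 0.01 = 0.04. Times 75 this is 3, and the noncentrality is 3/(1 − rho) = 4.29/6/10/15.

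| rho | 0.3 | 0.5 | 0.7 | 0.8 |
|---|---|---|---|---|
| Ordinary two-way ANOVA | 26% | 20% | 12% | 8% |
| With within-person term, F(2,296) | 44% | 58% | 81% | 94% |

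At rho 0.8 the ordinary-ANOVA figure is 7 to 8%, depending on the calculation. In the Hypothesis 2 subset (assumed cut at the mean, about 37 per arm) power is 17/17/14/15% without the term and 27/34/52/69% with it.

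**4. Change-score reading.** The 4- and 8-month changes share a baseline, so under compound symmetry they correlate 0.5 at any rho. The variance ratio for the group effect is 1.5, and type I error = 2·(1 − Φ(1.96/√1.5)) = 11%. A between-group pair of changes at one visit is not inflated: 5% unadjusted, about 1% with Tukey, about 2% for either visit. Power for either Tukey pair is 33/47/73/91%, against 43/57/81/94% for the gated contrasts in the fix.

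**5. County difference.** Assume a constant offset of 0.4 SD, no programme effect and a correct error term. The raw-score group test has noncentrality 0.16 × 75 × 3/[2(1 + 2·rho)] = 18/(1 + 2·rho) = 11.25/9/7.5/6.9. It rejects about 91/85/77/75% in simulation. The group-by-visit test stays near 5%.

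**6. Error control in the replacement.** Any false positive from the 4- and 8-month contrasts is about 9% ungated and 4.0 to 4.4% when gated by the 2-df test. For two Hypothesis 1 proportion tests it is about 10% unadjusted and 5% with Holm. The two hypotheses use different participants, so per outcome the chance is 1 − 0.95² = 9.75%.

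**7. Covariance.** Under AR(1) correlation φ, a pooled within-person error understates the variance of the 8-month contrast. The ratio is (1 − φ²)/[1 − (2φ + φ²)/3] = 1.29/1.38/1.46 for φ = 0.5/0.7/0.9. Simulated ungated null rejection is 8.2/9.4/10.7%, against about 5% with a contrast-specific error.

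**The case against.** The strongest reply is that two-way ANOVA is common shorthand for its repeated-measures version. The SAP names neither factors nor error term, and the participant codes make such an analysis feasible. This stands as far as it goes: on that reading the error rates in steps 1 to 4 do not apply. What remains is that the text does not say so, and that response, deciding effect and Hypothesis 1 analysis are still open. Step 5 shows why that matters even with correct errors.

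A reader might infer that the plan is certain to produce false positives. The documents do not support that. The inflated raw-score test is the group main effect, which is not what Hypothesis 2 asks; the raw-score test that does match is too strict. The change-score group F, at about 11%, is the one inflated test that would answer a question about change. If change scores with Tukey pairs were meant, the harm is lost power.

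It is also fair to say that this is a convenience-sample pilot and that every magnitude rests on assumed inputs. That softens the consequences. But Objectives states comparative hypotheses and the SAP declares significance at 0.05, so the rule must be interpretable.

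**Conclusion.** The concern holds as under-specification with a conditional error rate. What is certain is that the only stated test names no within-person term, no response and no deciding effect, and that Hypothesis 1 has no matching analysis.

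What is conditional is the size. If an ordinary ANOVA is run on raw scores, the test that matches Hypothesis 2 keeps only a fraction of its power and the group main effect is too liberal, to the extent shown above. Those figures depend on the assumed correlation, effect and compound symmetry. Only zero within-person correlation would make the ordinary raw-score F-tests correct, which is implausible for repeated measures on the same adults.

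It should be settled before analysis, because this is the trial's sole decision rule and the remedy is cheap.

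**What to change.** Replace the SAP sentence with the following.

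- **Model.** A linear mixed model for repeated measures with group, visit and group × visit, and an unstructured within-person covariance. Contrast-specific error terms are an alternative. A pooled-error mixed ANOVA without a sphericity correction is not (step 7).
- **Hypothesis 2 of each aim.** Fit the model among participants outside the recommended or normal range at baseline. The 2-df group-by-visit test at 0.05 decides for each outcome. Only if it is significant, test the between-group difference in change from baseline at 4 and at 8 months, each at 0.05 with a 95% CI. Drop the all-pairs Tukey.
- **Hypothesis 1 of each aim.** Among those within range at baseline, compare between groups the proportions still within range at 4 and at 8 months, with 95% CI and a Holm adjustment over the two visits.
- **Stated limits.** Error is held at 0.05 within each hypothesis for each outcome. It is not held across the two hypotheses (about 9.75% per outcome) or across outcomes. County confounding and regression to the mean remain: with a 0.4 SD county offset and no programme effect, the correct interaction test in the baseline-selected subset rejects about 10/8/7/6%.

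The cost is SAP wording and slightly more analysis, with no extra data. It does need each person's records linked across all three visits, and the documents differ on how long the name list survives. Subject Recruitment Methods & Privacy replaces names with codes once the September data are in, before the February 2019 visit. Informed Consent Process and Safety Precautions keep the list until post-survey data are entered, and Confidentiality sets deletion by January 2020. These sections should be reconciled.
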